6.3.2.1 Investigator Responsibilities for Reporting SAEs

The Investigator must immediately report to the Sponsor all SAEs, regardless of whether the Investigator believes they are drug related.

The Investigator must report all SAEs to the Drug Safety Contact person(s) within 24 hours of first becoming aware of the SAE. The Investigator must complete an SAE Form and include a detailed description of the SAE, as well as other available information pertinent to the case (e.g., hospital records, autopsy reports, and other relevant documents). The Investigator will keep a copy of this SAE Report Form on file at the study site.

The Investigator or study physician, after thorough consideration of all facts that are available, must include an assessment of causality of an AE to study medication in the report to the Sponsor.

Follow-up information, or new information available after the initial report, should be actively sought and reported to the Sponsor as it becomes available using the SAE Report Form.

The Drug Safety Contact for SAE reporting is:

6.3.2.2 Other Events Requiring Immediate Reporting

The Investigator must report a **pregnancy** that occurs in a subject during a clinical study to the Drug Safety Contact within 24 hours of first becoming aware of the event. Pregnancy should be reported on a Pregnancy Report Form. The Investigator should discuss the case with the Sponsor Medical Monitor; the Investigator must also follow any pregnant subject for 3 months after the child is born. Any AEs concerning the health of the subject during pregnancy or the child after birth must be documented and reported to the Sponsor.

Treatment-emergent **EPS** (e.g., akathisia, dystonia, parkinsonism, tardive dyskinesia), and neuroleptic malignant syndrome should in addition to documenting in the CRF, be reported to the Drug Safety Contact by faxing or scanning the appropriate completed form/source documentation within 24 hours of first becoming aware of the event. EPS incidence will be summarized and shared with study Investigators throughout the clinical trial.

Overdosage of molindone presumably may be manifested by severe EPS and sedation. Coma with respiratory depression and severe hypotension resulting in a shock-like syndrome could occur. In the event of a suspected overdose, the parent or legal representative should be instructed to call 911 or their local poison control center at

Symptomatic, supportive therapy should be the rule. Gastric lavage is indicated for the reduction of absorption of SPN-810, which is freely soluble in water. Since the adsorption of SPN-810 by activated charcoal has not been determined, the use of this antidote must be considered of theoretical value.

Emesis in a comatose patient is contraindicated. Additionally, while the emetic effect of apomorphine is blocked by SPN-810 in animals, this blocking effect has not been determined in humans.

6.3.2.3 Sponsor Responsibilities for Expedited Reporting of SAEs

The Sponsor will inform Investigators and regulatory authorities of ADRs that are both serious and unexpected, in compliance with applicable regulatory requirements, on an expedited basis (i.e., within specific time frames). For this reason, it is imperative that study sites submit SAE information to the Sponsor in the manner described above.

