6.3.1.1 Causality

AEs may be categorized as either adverse drug reactions or suspected adverse drug reactions (SADRs) based on their relationship to the study medication or procedure and the degree of certainty about causality.

SADRs are a subset of AEs for which there is evidence to suggest a causal relationship between the drug and the AE; i.e., there is a reasonable possibility that the drug caused the AE.

Adverse drug reactions (ADRs) are a subset of all AEs for which there is reason to conclude that the drug or procedure caused the event.

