6.3.1.4 Criteria for Assessing Causality

The Investigator is responsible for determining the relationship between the administration of study medication and the occurrence of an AE as **not suspected** or as a **suspected** reaction to study medication. These are defined as follows:

Not suspected: The temporal relationship of the AE to study medication administration makes a **causal relationship unlikely**, or other drugs, therapeutic interventions, or underlying conditions provide a sufficient explanation for the observed event.

- Not related: Temporal relationship to study medication administration is missing or implausible, or there is an evident other cause.
- Unlikely related: Temporal relationship to study medication administration makes a causal relationship improbable; and other drugs, chemicals, or underlying disease provide plausible explanations.

Suspected: The temporal relationship of the AE to study medication administration makes a causal relationship possible, and other drugs, therapeutic interventions, or underlying conditions do not provide a sufficient explanation for the observed event.

• **Possibly related:** Temporal relationship to study medication administration is plausible, but concurrent disease or other drugs or chemicals could also explain the event.

Information on medication withdrawal may be lacking or unclear. This will be reported as a **SADR**.

Definitely related: Temporal relationship to study medication administration is
plausible, and concurrent disease or other drugs or chemicals cannot explain the
event. The response to withdrawal of the medication (de-challenge) should be clinically
plausible. The event must be definitive pharmacologically or phenomenologically, using
a satisfactory re-challenge procedure if necessary. This will be reported as an adverse
drug reaction (ADR).

6.3.2 *Serious Adverse Events (SAEs)*

AEs are classified as serious or non-serious. An AE or ADR is considered "**serious**" if, in the view of either the Investigator or Sponsor, it results in one of the following outcomes:

- Death
- Life-threatening AE (I.e., the subject was at immediate risk of death from the AE as it occurred. This does not include an event that, had it occurred in a more severe form or was allowed to continue, might have caused death.)
- Inpatient hospitalization or prolongation of existing hospitalization

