7.6.1 Adverse Events

AEs will be classified into standardized medical terminology from the verbatim description (Investigator term) using the Medical Dictionary for Regulatory Activities (MedDRA V22.0). AEs will be summarized using discrete summaries at the subject and event level by system organ class and preferred term for each group of doses. Similarly, treatment-emergent AEs will be summarized by severity and relationship separately. Verbatim description and all MedDRA level terms, including the lower-level terms, for all AEs will be contained in the subject data listings.

All AEs occurring throughout the study period will be recorded. Treatment-emergent AEs (TEAEs) will be collected starting after the baseline fMRI scan and after the first dose of study medication (after Visit 3) to the end of the study. These AEs include those that emerge after the fMRI procedures and during treatment or worsen in severity during treatment. These AEs will be tabulated, listed, and analyzed.

Separate TEAE incidence tables will be presented for the 2 treatment groups. The incidence rates for all SADRs will also be summarized as described for all TEAEs.

In addition, these same tables will be presented by treatment period (Titration, Maintenance, and combined Titration and Maintenance periods). For the combined Titration and Maintenance periods, the incidence of TEAEs will also be presented by highest severity reported and the dose of study

medication at first occurrence. Listings (and tabular summaries, if warranted) of deaths, other SAEs, and other significant TEAEs, including TEAEs resulting in treatment discontinuation, will be provided.

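### The expedited-reporting sentence names only ADRs and the drug-reaction table names only SADRs, although the protocol attaches those labels to different causality grades

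*Protocol*

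**What the plan says.** **Definitions.** Protocol 6.3.1.1 opens by treating the two terms as alternatives: "AEs may be categorized as either adverse drug reactions or suspected adverse drug reactions (SADRs) based on their relationship to the study medication". A SADR is an event for which "there is a reasonable possibility that the drug caused the AE". An ADR is one for which "there is reason to conclude that the drug or procedure caused the event".

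**Grading.** Protocol 6.3.1.4 has the investigator class each event as not suspected or suspected. Only two grades sit under suspected. For possibly related, the instruction is "This will be reported as a SADR". For definitely related, it is "This will be reported as an adverse drug reaction (ADR").

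**Use of the terms.** Protocol 6.3.2.3 commits the sponsor as follows: "The Sponsor will inform Investigators and regulatory authorities of ADRs that are both serious and unexpected". The same sentence goes on to tie this to the regulatory rules that apply and to expedited timelines. It does not mention SADRs. For the analysis, SAP 7.6.1 says "The incidence rates for all SADRs will also be summarized as described for all TEAEs", and Protocol 8.3.1 has the same sentence. Neither mentions ADRs there.

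**The concern.** The two rules that depend on the causality label use different labels, and on the grading text neither label covers all suspected events.

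Two things are at stake:

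- **Safety communication.** Other investigators treating children need to know which events will be passed on to them. As worded, the named class leaves out serious unexpected events for which causation is a reasonable possibility but not established.
- **Reading of a safety table.** A table of SADR incidence by arm will be read as the incidence of drug reactions. If the label is applied as 6.3.1.4 writes it, the events with the strongest causal evidence are not in it, and the table will not agree with the summary of TEAEs by relationship.

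**Working it through.** The plan states no figure on this point, so the check sets the sections side by side.

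**Step 1: do the labels overlap?** Protocol 6.3.1.1 offers ADR and SADR as an either/or choice by degree of certainty. Protocol 6.3.1.4 gives each of the two suspected grades its own reporting label. Together the labels cover the suspected group without overlap. The counter-indication is that the SADR definition in 6.3.1.1, read alone, would also be met by a definitely related event, and both grades sit under one heading. Both readings are therefore carried forward, with a third in which ADR is used loosely in 6.3.2 for any drug-related event.

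**Step 2: apply each reading to the two rules.**

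| Reading | Expedited class named in 6.3.2.3 | SADR table (SAP 7.6.1, Protocol 8.3.1) |
|---|---|---|
| SADR = possibly only; ADR = definitely only | omits possibly related | omits definitely related |
| SADR = both grades; ADR = definitely only | omits possibly related | complete |
| ADR used loosely in 6.3.2 for both grades; SADR as graded in 6.3.1.4 | complete | omits definitely related |

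No single reading that keeps the grading labels of 6.3.1.4 makes both rules complete. The expedited-reporting gap survives the broad reading of SADR. The table gap does not.

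**Step 3: what the gaps do not touch.**

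- Protocol 6.3.2.1 sends every SAE to the sponsor within 24 hours, whatever its causality, so SAE capture is intact.
- SAP 7.6.1 also plans TEAE tables for both arms, a summary of TEAEs by relationship, and listings of all AEs. Definitely related events appear in all of these.

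**Step 4: size in the SADR table.** Protocol 4.1 plans 15 subjects per arm. A subject whose only suspected event is definitely related drops out of the numerator, so the arm's SADR incidence changes by 1/15 = 0.067, or about 6.7 percentage points. A subject who also has a possibly related event is still counted at subject level, so the overall SADR incidence does not change. The documents do not give the numbers reached before termination. In an arm of n subjects the change is 1/n.

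**The case against.** The strongest case on the other side is that this is loose terminology.

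- **ADR may be shorthand.** The opening of Protocol 6.3.2 defines seriousness for an AE or ADR without mentioning SADR, which suggests that ADR there means any drug-related event. This is a fair point about intent. It does not settle the wording, because 6.3.1.4 has just given ADR a narrower meaning.
- **The regulatory clause.** Section 6.3.2.3 ties expedited reporting to the applicable requirements, Protocol 10.2 commits the study to ICH GCP and the US regulations, and 10.1 provides for reportable AEs to go to the IRB. This stands in part. The clause may widen what is reported in practice, but it does not change the class named, and the documents do not say what the requirements cover.
- **Other channels.** Protocol 6.3.2.2 requires EPS and neuroleptic malignant syndrome to be reported within 24 hours and EPS incidence to be shared with investigators during the trial, whatever the label. This stands for those events only.
- **Early termination.** SAP 6.1 says the study ended early and all analyses are descriptive. This stands. An amendment to 6.3.2.3 can now change little.

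A reader might go further and infer that hardly any event could qualify for expedited notice, since the definitely related grade asks for no alternative explanation, a plausible response to withdrawal and, if needed, re-challenge. The documents give no figure for how often that grade would be used. A reader might also infer that drug-related incidence overall is understated. The by-relationship summary and the all-TEAE tables retain every such event, so any shortfall is confined to the SADR table. Nor do the documents show that any reportable event was withheld.

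**Conclusion.** The inconsistency is real and should be corrected. On the labels in Protocol 6.3.1.4, each of the two rules names one of the two suspected grades and leaves out the other: possibly related events from the expedited class, and definitely related events from the SADR table.

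The expedited-reporting half is the firmer of the two, because it holds whether SADR is read narrowly or broadly. It fails only if ADR changes meaning between 6.3.1.4 and 6.3.2.3, and what follows in practice depends on the regulatory requirements that the clause invokes. The table half rests on the non-overlapping reading of the labels, which the either/or wording and the separate reporting instructions favour but do not make certain.

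The consequence is limited. SAE capture is unaffected, no event disappears from the safety output as a whole, and the effect on the SADR table depends on how many subjects have only definitely related events, which the documents do not report.

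**What to change.** Reconcile the sections around one term:

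1. In Protocol 6.3.1.1 and 6.3.1.4, define SADR as every event classed as suspected, whether possibly or definitely related, with ADR as the definitely related subset.
2. In Protocol 6.3.2.3, replace ADRs with SADRs as the class that is expedited when serious and unexpected.
3. In SAP 7.6.1, state that the SADR incidence table includes both possibly and definitely related TEAEs, so that it agrees with the by-relationship summary. Protocol 8.3.1 should match.

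Since the study has ended, the third item is the main one still open. It needs one sentence in the SAP or a footnote to the table. Alongside it, the sponsor should check the SAE records and confirm that no serious, unexpected, possibly related event was left out of onward reporting to investigators and authorities.

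The cost is a few sentences and one check of existing records. It needs no new data and changes no treatment rule. In an ongoing trial, the second item could bring a few more events into expedited notice.

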6.3.3 Management of Treatment-Emergent Extrapyramidal Symptoms

If a subject experiences treatment-emergent EPS (including akathisia, dystonia, parkinsonism, or tardive dyskinesia), benztropine will be permitted at a starting dose of 0.5 mg BID up to a range of 1 to 4 mg/day. Lorazepam (1 to 2 mg per dose not to exceed 3 times daily) and clonazepam (0.25 to 1 mg per dose not to exceed twice daily) will also be permitted to treat the occurrence of EPS. For the treatment of akathisia, propranolol is recommended up to 90 mg/day in divided doses, 3 times per day, starting at 10 mg twice daily and up to 30 mg three times daily, as needed.

A positive finding on an EPS safety assessment scale (Barnes Akathisia Rating, Simpson-Angus, or AIMS) does not necessarily equate to an EPS event. Investigators should evaluate positive findings on the EPS safety assessment scales and integrate them into a global clinical observation to determine if an AE of EPS should be recorded.

6.3.4 Laboratory Measurements

With the exception of urine pregnancy tests, clinical laboratory tests will be performed by a central laboratory as specified in the reference binder.

Details for collecting, handling, and shipping samples (including shipment addresses) will be described in a separate laboratory manual. The Schedule of Visits and Procedures (Table 1) shows the time points at which urine samples will be collected for urinalysis and blood samples will be collected for clinical laboratory tests and plasma concentration levels.

Table 3 presents the clinical laboratory tests to be performed. Metabolic parameters (including insulin, glucose, triglycerides, and cholesterol) and prolactin will be measured.

All laboratory tests will be reviewed in a timely manner by qualified site personnel to ensure safety. Abnormal lab findings may be confirmed if necessary by one repeated test at the discretion of the Investigator. Any laboratory abnormality may qualify as an AE in the Investigator's judgment.

A total of approximately 42 mL of blood per subject will be drawn during the study: 22 mL is for clinical laboratory tests and 20 mL is for PK sampling.

Table 3: Clinical Laboratory Tests

Category	Parameters
Hematology	WBC with differential (neutrophils, lymphocytes, monocytes, eosinophils, basophils, large unstained cells), Hgb, HCT, RBC, MCH, MCHC, MCV, and platelet count

Chemistry	Electrolytes: Na ⁺ , K ⁺ , chloride, bicarbonate			
	Liver function tests: alkaline phosphatase, AST, ALT, total bilirubin, direct bilirubin, indirect bilirubin			
	Renal function parameters: BUN, creatinine			
	Other: glucose, Ca ²⁺ , albumin, phosphorus, lactate dehydrogenase, total protein, CK/CPK, globulin, uric acid, triglycerides, insulin, prolactin, cholesterol (total, HDL, and LDL), amylase, GGT, iron, lipase, and magnesium			
Urinalysis	Glucose, protein (total), ketones, bilirubin, urobilinogen, hemoglobin, leukocyte esterase, nitrite			
Urine drug test	Cocaine, amphetamines, barbiturates, benzodiazepines, cannabinoids, opioids, phencyclidine, propoxyphene, methadone and alcohol			
Urine pregnancy test (FOCP only)	hCG			

ALT: alanine transaminase; AST: aspartate transaminase; BUN: blood urea nitrogen; CK/CPK: creatinine kinase/creatinine phosphokinase; FOCP: females of childbearing potential; GGT: gamma glutamyl-transferase; hCG: human chorionic gonadotropin; HCT: hematocrit; HDL: high-density lipoprotein; Hgb: hemoglobin; LDL: low-density lipoprotein; MCH: mean corpuscular hemoglobin; MCHC: mean corpuscular hemoglobin concentration; MCV: mean corpuscular volume; RBC: red blood cells; WBC: white blood cells.

6.3.5 Vital Signs and Height/Weight Measurements

Vital signs' measurements (e.g., blood pressure, heart rate, temperature, and respiratory rate) and height, weight, and BMI will be obtained at visits designated on the Schedule of Visits and Procedures (Table 1). Blood pressure and heart rate will be measured after the subject has been sitting for 5 minutes. Vital signs may be taken at any other time, as deemed necessary by the Investigator.

6.3.6 *Medical History*

Medical history will be collected at visits designated on the Schedule of Visits and Procedures (Table 1).

6.3.7 Physical Examinations and Electrocardiograms (ECGs)

A complete physical examination will be conducted at visits designated on the Schedule of Visits and Procedures (Table 1). This will include assessments of the head, eye, ears, nose, throat, skin, thyroid, abdomen (liver and spleen), lymph nodes, and extremities and the cardiovascular and nervous systems (motor strength, cranial nerves, deep tendon reflexes, coordination, balance, and gait).

6.3.8 *Electrocardiograms*

A 12-lead ECG will be obtained at visits designated on the Schedule of Visits and Procedures (Table 1). Additional ECGs may be performed at other times if deemed necessary by the Investigator. The ECG will be recorded while the subject is resting in a supine position. The ECG will electronically calculate the heart rate and will measure the PR, QRS, QT, and QTc intervals.

All ECG tracings will be reviewed within 24 hours by the Investigator or qualified Sub-Investigator. PR intervals will be determined for each of these ECGs from a single reading. Invalid measurements will be repeated. QTc will be reported as QTcF (QT corrected using Fridericia's method).

6.3.9 Special Safety Assessments

The following special scales will be administered in the clinic at visits designated in the Schedule of Visits and Procedures (Table 1):

6.3.9.1 Simpson-Angus Scale (Section 12.3)

The Simpson-Angus Scale is a 10-item rating scale that is widely used for assessment of neuroleptic-induced parkinsonism (Simpson & Angus, 1970). It consists of 1 item measuring gait, 6 items measuring rigidity, and 3 items measuring glabella tap, tremor, and salivation, respectively. This assessment will be administered at Visit 1, Visit 4, and Visit 6.

6.3.9.2 Barnes Akathisia Rating Scale (BARS) (Section 12.4)

The BARS is a rating scale for drug-induced akathisia and includes components for rating the observable, restless movements characteristic of akathisia, the awareness of restlessness, and any distress associated with the condition (Barnes, 1989). This assessment will be administered at Visit 1, Visit 4, and Visit 6.

6.3.9.3 Abnormal Involuntary Movement Scale (AIMS) (Section 12.5)

The AIMS test is a rating scale used to measure tardive dyskinesia (Munetz & Benjamin, 1988). There are 12 items that rate involuntary movements of various areas of the subject's body. This assessment will be administered at Visit 1, Visit 4, and Visit 6.

6.3.9.4 Columbia-Suicide Severity Rating Scale (C-SSRS) (Section 12.6)

The C-SSRS is a questionnaire that prospectively assesses suicidal ideation and behavior using a semi-structured interview to probe patient responses (Posner et al., 2011). The C-SSRS versions applicable to the current study are the Baseline version and the Since Last Visit version (Visit 1, Visit 4 and Visit 6).

The Baseline version of the scale assesses lifetime suicidal ideation and behavior. This version is suitable as part of a subject's first interview and will be used at Visit 1 to identify volunteers who must not participate in the trial due to their suicidal tendencies.

The Since Last Visit version of the scale assesses any suicidal thoughts or behaviors the subjects may have had since the last administration of the C-SSRS. This version will be used for the other study visits.

6.4 Tertiary Variables

6.4.1 Pharmacokinetic Measurements

6.4.1.1 Pharmacokinetic Variables

The pharmacokinetic variables of interest will be (but not limited to) the following:

- 1. Apparent clearance (CL/F),
- 2. Apparent volume of distribution (V/F) of molindone in the study population

6.4.2 Clinical Global Impression Scale (Section 12.1)

The Clinical Global Impression scale was developed to provide a brief, stand-alone assessment of the clinician's view of a subject's global functioning prior to and after administration of a study medication (Guy, 1976). Severity of illness (CGI-S) and global improvement (CGI-I) are both rated on a scale of 1 to 7, with 7 being "extremely ill" or "very much worse," respectively. Successful therapy is indicated by a lower overall score in subsequent testing. Investigators should consider their total clinical experience with children who have ADHD and associated feature of IA and rate how severe the subject's condition is at the time.

CGI-S will be evaluated by the Investigator on a 7-point scale with 1=Normal,
 2=Borderline ill, 3=Mildly ill, 4=Moderately ill, 5=Markedly ill, 6=Severely ill, and
 7=Extremely ill.

CGI-S will be administered by the Investigator at Visit 1, Visit 4, and Visit 6.

 CGI-I will be evaluated by the Investigator on a 7-point scale with 1=Very much improved, 2=Much improved, 3=Minimally improved, 4=No change, 5=Minimally worse, 6=Much worse, and 7=Very much worse.

CGI-I will be administered by the Investigator at Visit 4 and Visit 6.

